1.3 Aims and hypotheses

The research goals of this randomized controlled trial are to determine the feasibility and the mechanism of change of iMBT that has been developed using the Acceptance Checklist for Clinical Effectiveness Pilot Trials (ACCEPT) framework³⁵.

The primary research question is as follows:

- What is the effectiveness of the iMBT in relation to improvements on depressive symptoms among people with clinical depression, relative to a usual care control after the intervention and in 3-month follow-up?

Secondary questions include the following:

- Which facet(s) of mindfulness (i.e., observe, describe, act with awareness, non-react and non-judgement) improved during the intervention?
- How does the growth trajectory of different facets of mindfulness relate to the improvement of well-being and reduction of ill-being?

We hypothesize that:

- H1 Participants in iMBT group will have greater reduction in depressive symptoms and increase in all facets of mindfulness and mental well-being, than the usual care group at post-intervention, and 3-month follow-up.
- H2 Using latent growth analysis, the intraindividual growth trajectory of the monitor and acceptance facets of mindfulness would mediate the effect of iMBT on the intraindividual changes in depressive symptoms.
- H3 Using multi-group analysis, in accord with Acceptance and Monitor theory, the relationship between the growth trajectory of monitor facets of mindfulness and the growth trajectory of depressive symptoms will be moderated by the level of acceptance. People with greater acceptance of inner experience will benefit more from the change of monitor facets of mindfulness in iMBT.

References

1. FerrariAJ, SomervilleAJ, BaxterAJ, et al. Global variation in the prevalence and incidence of major depressive disorder: A systematic review of the epidemiological literature. *Psychol Med*. 2013. doi:10.1017/S0033291712001511
2. LiuQ, HeH, YangJ, FengX, ZhaoF, LyuJ. Changes in the global burden of depression from 1990 to 2017: Findings from the Global Burden of Disease study. *J Psychiatr Res*. 2019. doi:10.1016/j.jpsychires.2019.08.002
3. PatelV, ChisholmD, ParikhR, et al. Addressing the burden of mental, neurological, and substance use disorders: Key messages from Disease Control Priorities, 3rd edition. *Lancet*. 2016. doi:10.1016/S0140-6736(15)00390-6

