2.4 Analytical procedure

2.4.1 Efficacy analyses of iMBT on Depressive symptoms, Mindfulness, and Mental Well-being

Significance testing of baseline group equivalence will be conducted using Analysis of variance (ANOVA) and chi square test if the variables consisted of nominal data.

To investigate the efficacy of iMBT, intention-to-treat (ITT) linear mixed models using restricted maximum likelihood (REML) estimation will be conducted for each outcome measure.

Fixed factors of time, group, and time*group will be entered in each model. Within-group effect size will be computed for pre(T0)-to-post(T3), and pre(T0) to follow-up(T4) changes on each outcome measures, and between-group effect sizes (Hedge's g) will be computed at post(T3) and follow-up(T4). Reliable change scores were calculated⁶ between pre(T0)and post(T3)-intervention, as well as between pre(T0)and follow-up(T4) for the PHQ-9, to determine rates of clinically reliable improvement and deterioration. All analyses will be performed in SPSS version 24.

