2.5 Feasibility

Given that our laboratory has already developed the prototype of the iMBT, it is anticipated that this trial will be completed within a 2-year period, with approximately 70% of participants retained. This is in line with similar e-psychotherapy studies where one meta-analysis reported an average of 23% dropout.

References

1. SchulzKF, AltmanDC, MoherD. CONSORT 2010 Statement: Updated guidelines for reporting parallel group randomised trials. *Ital J Public Health*. 2010. doi:10.4178/epih/e2014029
2. SheehanDV., LecrubierY, SheehanKH, et al. The Mini-International Neuropsychiatric Interview (M.I.N.I.): The development and validation of a structured diagnostic psychiatric interview for DSM-IV and ICD-10. In: *Journal of Clinical Psychiatry*. ; 1998.
3. MakWWS, TongACY, YipSYC, et al. Efficacy and moderation of mobile app–Based programs for mindfulness-Based training, self-Compassion training, and cognitive behavioral psychoeducation on mental health: Randomized controlled noninferiority trial. *J Med Internet Res*. 2018. doi:10.2196/mental.8597
4. StoneAB. Mindfulness-Based Cognitive Therapy for Depression: A New Approach to Preventing Relapse. *Psychiatr Serv*. 2005. doi:10.1176/appi.ps.56.9.1165
5. SpijkermanMPJ, PotsWTM, BohlmeijerET. Effectiveness of online mindfulness-based interventions in improving mental health: A review and meta-analysis of randomised controlled trials. *Clin Psychol Rev*. 2016. doi:10.1016/j.cpr.2016.03.009
6. JacobsonNS, TruaxP. Clinical Significance: A Statistical Approach to Defining Meaningful Change in Psychotherapy Research. *J Consult Clin Psychol*. 1991. doi:10.1037/0022-006X.59.1.12
7. ByrneBM. *Structural Equation Modeling with AMOS: Basic Concepts, Applications, and Programming, Second Edition.*; 2013. doi:10.4324/9780203805534
8. DuncanTE. *An Introduction to Latent Variable Growth Curve Modeling.*; 2013. doi:10.4324/9780203879962
9. MacKinnonDP, LockwoodCM, WilliamsJ. Confidence limits for the indirect effect: Distribution of the product and resampling methods. *Multivariate Behav Res*. 2004. doi:10.1207/s15327906mbr3901_4
10. HuLT, BentlerPM. Cutoff criteria for fit indexes in covariance structure analysis: Conventional criteria versus new alternatives. *Struct Equ Model*. 1999. doi:10.1080/10705519909540118

7. Working Schedule

- | | | |
|---------------------------------|----------------------|--------------|
| a) Start Date: | June 30, 2020 | (DD/MM/YYYY) |

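### Between-group Hedges' g at T3 and T4 reads as an unadjusted level comparison, while H1 and the time-by-group term concern change from T0; one T0-adjusted contrast should serve as both test and effect size

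*Protocol*

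**What the plan says.** Section 2.4.1 of the protocol words its two kinds of effect size differently. For the within-group kind: "Within-group effect size will be computed for pre(T0)-to-post(T3), and pre(T0) to follow-up(T4) changes on each outcome measures". The between-group kind, Hedges' g, "will be computed at post(T3) and follow-up(T4"). The first names changes; the second names only time points.

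The efficacy model in the same section is an intention-to-treat linear mixed model fitted by REML: "Fixed factors of time, group, and time*group will be entered in each model". It lists no T0 covariate and does not constrain the T0 means to be equal. T0 differences are otherwise addressed only by a test: "Significance testing of baseline group equivalence will be conducted using Analysis of variance (ANOVA"). No adjustment follows from it.

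Section 1.3 states H1 as a difference between arms in change: "Participants in iMBT group will have greater reduction in depressive symptoms and increase in all facets of mindfulness and mental well-being". Section 2.3 gives f = 0.11, 80% power and a total of 116. Section 2.1 gives 1:1 allocation. Section 2.5 expects the trial to finish "with approximately 70% of participants retained", without naming the visit.

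**The concern.** With T0 as one of the time levels and T0 means free to differ, the time-by-group term measures how far the arms differ in change. A g computed on T3 or T4 levels measures something else in the sample at hand. Nothing in section 2.4.1 ties the two together.

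The between-group g is the figure that readers and later meta-analyses will take from this trial. In a trial of 116 that expects a small effect, a chance T0 difference can be as large as the effect itself. The report could then show an effect size and an interaction that point in different directions, with no rule for which one expresses the result.

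**Working it through.** **Inputs from the protocol.** Total N = 116, hence 58 per arm at 1:1; f = 0.11; 80% power.

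**Assumptions.** Two-sided alpha 0.05. Correlation rho between T0 and T3 (or T4) of 0.3 to 0.7; the protocol gives none. Unit SD at each visit. True effect 0.22 SD, which is f = 0.11 read as a plain two-group difference (d = 2f). No missing data unless stated.

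**The plan's own figure.** Take a within-between interaction with m = 4 measurements and rho = 0.5:
- lambda = f² × N × m / (1 - rho) = 0.0121 × 116 × 4 / 0.5 = 11.23, with 3 and 342 degrees of freedom. Power is 80.8%.
- The smallest even N reaching 80% is 114, close to the stated 116.
- A between-groups main effect at rho 0.5 needs 392 to 490 in total for 5 down to 2 measurements. Two means at d = 0.22 need 650.

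So the sample size fits a test of change, not one of levels.

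**How the contrasts relate.** Orient scores so that positive favours iMBT. Let D0 be the chance difference between arms at T0 and delta the true effect.
- Identity: level difference = change difference + D0.
- Mean level difference given D0: delta + rho × D0.
- Mean change difference given D0: delta - (1 - rho) × D0.
- T0-adjusted difference: delta, whatever D0 is.

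**Size of D0.** SD = sqrt(2/58) = 0.186; 95% range ±1.96 × 0.186 = ±0.36. The chance that |D0| exceeds 0.20 is 28%.

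**Example.** rho = 0.5, delta = 0.22, D0 = 0.20 against iMBT:
- level: 0.22 - 0.5 × 0.20 = 0.12
- change: 0.22 + 0.5 × 0.20 = 0.32
- T0-adjusted: 0.22

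**Standard errors at 58 per arm.** Level: sqrt(2/58). Change: level SE × sqrt(2(1 - rho)). T0-adjusted: level SE × sqrt(1 - rho²).

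| rho | level | change | T0-adjusted | adjusted vs level: 1 - sqrt(1 - rho²) |
|---|---|---|---|---|
| 0.3 | 0.186 | 0.220 | 0.177 | 5% smaller |
| 0.5 | 0.186 | 0.186 | 0.161 | 13% smaller |
| 0.7 | 0.186 | 0.144 | 0.133 | 29% smaller |

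**Disagreement in sign.** With delta = 0.22, 20,000 simulated trials per setting gave opposite signs for the level and change contrasts in 15.9%, 15.4% and 14.4% of trials at rho 0.3, 0.5 and 0.7. The bivariate normal calculation gives 16.0%, 15.4% and 14.0%.

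**Changing g alone is not enough.** If g were T0-adjusted while the test stayed an unadjusted change contrast, the two would still have opposite signs in 11%, 8% and 4% of trials at rho 0.3, 0.5 and 0.7 (same bivariate normal calculation). The mismatch goes only when one contrast serves both purposes.

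**The case against.** The best defence has four parts.

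1. **The formula is not fixed.** Section 2.4.1 fixes the time points of g and leaves open observed or model means, the choice of SD and any adjustment. A statistical analysis plan may settle these. This stands in part: the level reading is an inference from the contrast in wording. But the listed model has no T0 adjustment, so model means from it would give the same level contrast.

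2. **There is no contradiction with H1.** H1 compares the arms at post-intervention and follow-up, and under randomisation level and change target the same effect. This stands. The fault is mismatch and avoidable imprecision. Section 2.4.1 also does not name time-by-group as the decisive test, and taken over all visits that term has several degrees of freedom, so it need not match a contrast at one visit.

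3. **Change is no gold standard.** This stands. At rho 0.5, level and change each have the wrong sign in about 12% of trials. A reader might infer that the level g contains the whole T0 difference as error, or that a change-score g would cure the problem. Neither follows: the whole of D0 is only the gap between the two contrasts, and the change contrast errs too.

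4. **Dropout bias is not shown.** A reader might infer that g will be biased by loss to follow-up. That would need g to come from observed scores, which would leave the declared intention-to-treat basis, and dropout that depends on scores in a particular way. The protocol states neither. Figures for such a bias would reflect assumed dropout slopes and directions.

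Counts of disagreement on significance also add little, because no test of g is planned. The planned within-group effect sizes and PHQ-9 reliable change scores make change visible, but they do not give an adjusted comparison of arms.

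**Conclusion.** The point holds as a mismatch worth correcting. On the natural reading, the planned between-group g and the change contrast behind H1 and the time-by-group term are two different unadjusted estimators of one effect, separated by a chance T0 difference with SD 0.186 at 58 per arm. With a true effect of 0.22 SD they point in opposite directions in about one trial in six or seven.

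This rests on reading g as an unadjusted level comparison, on rho between 0.3 and 0.7, on 0.22 as the true effect, and on full data. It does not show that the efficacy analysis is invalid or that g is systematically biased. It should be changed because a baseline that is collected anyway gives a more precise estimate and makes test and effect size agree.

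**What to change.** In section 2.4.1, define one contrast and use it twice. For example:

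*At T3 and at T4, the efficacy test is the difference between arms estimated from the linear mixed model with adjustment for T0 (T0 as a covariate, or T0 means constrained to be equal in the two arms). The between-group g is this same estimate divided by one pre-stated pooled SD, reported with the 95% confidence interval from the model. Within-group effect sizes are descriptive.*

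Once T0 is adjusted for, level and change give the same contrast, so the choice between them disappears. Taking g from the model also keeps it on the intention-to-treat basis.

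The cost is a modest change of model specification and no new data. The resulting g is less directly comparable with papers that report raw post-score g; observed means and SDs by arm and visit can be tabulated beside it for that purpose.

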2.4.2 Mechanism of the iMBT: Parallel process growth modelling

To investigate which facet(s) of mindfulness mediate(s) the therapeutic effect of iMBT, parallel process growth modelling will be used. Structural equation modelling (AMOS, version 26.0) will be used to compute the latent growth curve models^{7,8}. Latent growth curve modelling is a longitudinal analysis that analyzes growth over a period of time. Each growth curve has a latent baseline (the intercept) and a growth rate over time (the slope). LGM here will be used to characterize the overall trajectories of change (slope) of all five facets in mindfulness. How changes in each facets of mindfulness covaries between conditions, and the extent to which changes in each facets of mindfulness (putative mediators) mediates the effects of iMBT on changes in mental health outcomes will be analyzed. Quadratic growth factors will be added to the models to better estimate the trajectory shape when necessary.

To assess the existence of a mediating indirect effect from intervention allocation to the mental health outcome via the putative mediators, we will combine the growth model for the metal health outcome and the growth model for each putative mediators model into a combined parallel process growth model (see Fig 2). We will test the product of (a) the effect of treatment allocation on the growth of the mediator and (b) the effect of growth on the mediator on the growth rate on the outcome. The ab-product's confidence intervals will be estimated based on bootstrapping of 1000 samples⁹.

[figure not shown]

Figure 2. Parallel process growth model to assess statistical mediation over slopes. Rectangles denote observed variables and ellipses denote for latent variables. PMR = putative mediator (i.e. five facets in mindfulness which include observe, describe, act with awareness, non-react and non-judgement) MHO= mental health outcome (i.e. depressive symptoms, well-being, and difficulties in emotion regulation) T0,T1,T2 and T3 = Assessment at week 0,2,4 and 6. Bolded arrows highlighted the path of primary interest, which include the path from treatment allocation, (a)to growth in the putative mediator, to growth in the mental health outcome (i.e., the ab-product).

The adequacy of the models will be examined the following goodness of fit indices: comparative fit index (CFI), Tucker and Lewis index (TLI), and incremental fit index (IFI), which indicate a good adjustment to empirical data when around 0.95, and the standardized root mean squared residual (SRMR), which indicates a good adjustment when <0.08 ¹⁰.

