2.3 Power Calculation and Sample Size

Based on past research⁵, we expected a small to medium ($f = 0.11$) difference between the iMBT and the TAU control group. Thus, using G * Power software (version 3.1.9.2), a sample size of 116 will be needed to detect superiority of the intervention groups over the TAU control group with 80% power.

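### Where a quadratic factor is added, the slope-on-slope ab product describes the rate of change at week 0, not the mediated T0–T3 change

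*Protocol*

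**What the plan says.** Section 2.4.2 defines the growth factors thus: "Each growth curve has a latent baseline (the intercept) and a growth rate over time (the slope"). The caption to Figure 2 gives the occasions in the growth model: "T0,T1,T2 and T3 = Assessment at week 0,2,4 and 6". These are four equally spaced waves.

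The mediation test is a single product. Path a is "the effect of treatment allocation on the growth of the mediator", and path b is "the effect of growth on the mediator on the growth rate on the outcome". The caption describes the whole as "Parallel process growth model to assess statistical mediation over slopes". Inference rests on a bootstrap: "confidence intervals will be estimated based on bootstrapping of 1000 samples".

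The paragraph on trajectories ends: "Quadratic growth factors will be added to the models to better estimate the trajectory shape when necessary". The next paragraph combines the mediator and outcome growth models into the mediation model. Nothing there says that ab is redefined, that time is re-centred, or that the quadratic factor enters the indirect effect.

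**The concern.** In a straight-line growth model the slope is the change per interval throughout, so a product of slope effects is a mediated change over the intervention. With a quadratic factor and time zero at baseline, the linear factor becomes the tangent to the curve at T0. Whatever the curve does afterwards is carried by the quadratic factor, which a product taken over slopes does not use.

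H2 in section 1.3 and the aim in 2.4.2 of finding which facets mediate both depend on these products. Two things are at stake:

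- A facet that moves late in the six weeks has a small initial rate. It could therefore give an ab near zero despite a real group difference by T3.
- One facet's ab could describe six-week change while another's describes the rate at week 0, although both would be reported under the same name.

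The bootstrap does not help, because it puts an interval around whichever quantity ab happens to be. The fit indices at the end of 2.4.2 do not help either. With unrestricted growth factors, moving the time origin leaves fit unchanged but changes the linear factor.

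**Working it through.** **The plan's own figures.** The mediation analysis has no numerical figure to reproduce. The only computed figure in the plan is the total of 116 in section 2.3, for which "we expected a small to medium ($f = 0.11$) difference between the iMBT and the TAU control group". With assumed settings (within-between interaction, four occasions, correlation 0.5, sphericity, two-sided 5%) I get 114 for 80% power, and power 0.808 at 116. That is close enough, and it has no bearing on this point.

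**Inputs from section 2.4.2.** Weeks 0, 2, 4 and 6, scored t = 0, 1, 2, 3; intercept at baseline, so t = 0 at T0; ab on the slopes.

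**Assumptions.** The loadings are not printed, so T0 coding is inferred from the intercept being the baseline. The path b is taken to be the same for the linear and quadratic parts. The curve shapes are illustrations, each with a T0–T3 group difference of 3 units (1.0 per interval).

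**Algebra.** Write the group difference in the mediator as d(t) = a_s·t + a_q·t².

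- Linear factor with T0 coding: d′(0) = a_s.
- Mean change per interval over T0–T3: [d(3) − d(0)]/3 = (3a_s + 9a_q)/3 = a_s + 3a_q.
- Ratio of ab on slopes to mediated change per interval: a_s·b / [(a_s + 3a_q)·b] = a_s/(a_s + 3a_q).

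| Shape of group difference | a_s | a_q | Values at T0, T1, T2, T3 | a_s + 3a_q | Ratio |
|---|---|---|---|---|---|
| Straight line | 1 | 0 | 0, 1, 2, 3 | 1 | 1.0 |
| Mild slowing | 1.3 | −0.1 | 0, 1.2, 2.2, 3.0 | 1 | 1.3 |
| Levels off at T3 | 2 | −1/3 | 0, 1.67, 2.67, 3 | 1 | 2.0 |
| Starts flat, then accelerates | 0 | 1/3 | 0, 0.33, 1.33, 3 | 1 | 0 |
| Peaks before T3 | 3 | −2/3 | 0, 2.33, 3.33, 3 | 1 | 3.0 |
| Curve dips between T0 and T1 | −0.5 | 0.5 | 0, 0, 1, 3 | 1 | −0.5 |

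**Why straight-line models escape.** The least-squares slope of t² on t over 0, 1, 2, 3 is [(−1.5)(0) + (−0.5)(1) + (0.5)(4) + (1.5)(9)]/5 = 15/5 = 3. A straight line fitted to the curve therefore has slope a_s + 3a_q, which is the mean T0–T3 change per interval.

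**Simulation check.** Growth factors were simulated for 400,000 persons with b = −0.5, so the true mediated change is −0.50 per interval. The slope product in the T0-coded quadratic model was −1.00 for the curve that levels off and 0.00 for the one that starts flat. The straight-line slopes of the same curves gave −0.50 for both. This confirms the algebra on the factors themselves. It is not a fit of the planned model at the planned sample size.

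**Check of the remedy.** Since a_s·t + a_q·t² = (a_s + 3a_q)·t + a_q·t(t − 3), quadratic loadings of t(t − 3) = 0, −2, −2, 0 make the linear factor equal to a_s + 3a_q. It is then 1 for every row of the table, and the intercept stays at T0.

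**The case against.** The strongest case against is that the faulty quantity is inferred. The protocol never says outright that the linear factor alone carries ab once a quadratic is present, Figure 2 is not shown, and no loadings are given. The sentence on quadratics belongs to the description of trajectories. Centring time at week 3 would remove the problem. The time coding and the criterion for adding a quadratic are also things a statistical analysis plan may settle.

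Some of this stands. The missing criterion is not raised here, and T0 coding is an inference. But the text ties the intercept to baseline, which centring at week 3 would contradict. It takes mediation over slopes, and it adds quadratics to the same models that are then combined. Followed as written, it gives the wrong quantity in that branch. This goes beyond missing detail.

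It is also fair that the default linear model is sound, that ratios of 2 and 0 need pronounced curvature, and that exact zero needs the groups to start with no difference in rate. For a facet that changes early, ab is rescaled, but mediation is not created where there is none.

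A reader might infer that the plan would misrank the facets. The documents do not support that, because they assess whether an indirect effect exists for each mediator and state no ranking.

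**Conclusion.** Wrong as written, but only in the conditional quadratic branch of the secondary mediation analysis. In that branch ab on the slopes misstates mediated T0–T3 change by a_s/(a_s + 3a_q): near 1 for slight curvature, 1.3 for mild slowing, 2 for levelling off at T3, and 0 for a flat start. The more serious consequence is a missed mediator when change comes late. The other is that ab has no common meaning across models with and without the quadratic.

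The conclusion rests on time being zero at T0, which is implied rather than printed, on ab staying on the linear slope, and on a common b.

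A reader might take doubling or vanishing as the expected error, or as its limits. It is neither. Those values belong to two chosen shapes, other shapes gave 3.0 and −0.5, and the documents say nothing about which shape to expect. Nor does the point reach the linear growth models or the mixed-model efficacy analysis in section 2.4.1.

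**What to change.** State in section 2.4.2, before the data are analysed, that the indirect effect is defined on model-implied T0–T3 change in mediator and outcome, for every facet and every outcome, whether or not a quadratic is added. One simple way is to keep linear loadings 0, 1, 2, 3 and code the quadratic loadings as t(t − 3) = 0, −2, −2, 0. The intercept then remains the baseline, and the linear slope is the mean T0–T3 change per interval.

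Freed time scores (T0 = 0, T3 = 1, the two middle scores estimated) could be a sensitivity analysis. The plan should note that they assume one trajectory shape across people and across both arms.

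The cost is a sentence or two in the protocol and slightly more model specification work. No data collection changes.

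### Section 2.4.2 asks which mindfulness facets mediate, but one-facet growth models (its most natural reading) cannot by themselves separate facets whose slopes are correlated within arm

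*Protocol*

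**What the plan says.** The question in section 2.4.2 is facet-specific: "To investigate which facet(s) of mindfulness mediate(s) the therapeutic effect of iMBT, parallel process growth modelling will be used". The background (section 1.2) gives the reason: naming mindfulness as a whole as the mechanism is not informative enough, so the facets are to be examined one by one.

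The model is built by combining the growth model for the outcome with "the growth model for each putative mediators model into a combined parallel process growth model (see Fig 2". The tested product is made of "the effect of treatment allocation on the growth of the mediator" and the path from that mediator's growth to the outcome's growth. The Figure 2 legend gives the route of interest as leading "to growth in the putative mediator, to growth in the mental health outcome (i.e., the ab-product". It has one mediator slot, to be filled by the "five facets in mindfulness which include observe, describe, act with awareness, non-react and non-judgement", and one outcome slot, to be filled by "depressive symptoms, well-being, and difficulties in emotion regulation".

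H2 (section 1.3) expects that "the intraindividual growth trajectory of the monitor and acceptance facets of mindfulness would mediate the effect of iMBT". H1 expects an "increase in all facets of mindfulness and mental well-being" relative to usual care. H3 is a multi-group moderation hypothesis and does not separate indirect effects. Nowhere does the protocol describe a model that holds several facet slopes at once, lets them covary, or compares their indirect effects.

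**The concern.** Randomisation protects path a (allocation to facet slope). It does not protect path b (facet slope to outcome slope), because facet slopes are not randomised. If two facets tend to change together in the same person, a model with only one of them credits it with part of what the other does. A facet with no effect of its own can then show a non-zero ab product.

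This bears on H2. Separate models could support mediation by both the monitor and the acceptance facets when only one acts. The mechanism is one of the trial's two aims, and its result is meant to guide refinement of iMBT. The primary efficacy analysis in section 2.4.1 is not affected.

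**Working it through.** **1. Inputs from the protocol.** N = 116 with 80% power for f = 0.11 (section 2.3); 1:1 allocation (2.1); about 70% retained (2.5), so 0.70 × 116 = 81.2, run as 82 for equal arms; five facets, three outcomes, bootstrap intervals for ab (2.4.2). The protocol gives no power figure for mediation, no correlation between facet slopes and no facet effect.

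The stated 116 belongs to the efficacy comparison. It is nearly reproduced as a group-by-time interaction with four measures, correlation 0.5 and two-sided alpha 0.05 (all three assumed): λ = f²·N·m/(1-ρ) = 0.0121 × 116 × 4 / 0.5 = 11.2, power 0.808, smallest even N = 114. The present point does not depend on it.

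**2. Expected bias.** Let X be allocation, A a facet that acts and O a facet that does not:

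- A = aX + e₁, O = aX + e₂, residual SD 1, corr(e₁, e₂) = r
- Y = bA + noise

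Regressing Y on X and O gives O the coefficient r·b, so its expected product is a·r·b; the true value is 0. The acting facet has a·b.

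| | r = 0.3 | r = 0.5 | r = 0.7 | acting facet |
|---|---|---|---|---|
| a = 0.5, b = -0.5 | -0.075 | -0.125 | -0.175 | -0.25 |
| a = 0.22, b = -0.5 | -0.033 | -0.055 | -0.077 | -0.11 |

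Simulated means for the first row were -0.073, -0.129 and -0.177. As a share of the acting facet's product the bias is r, whatever a and b are. At r = 0 it vanishes, even though treatment moves both facets.

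**3. How often the inert facet is flagged in a one-facet model.** Simulation on observed slopes with allocation in the outcome equation; flagged means that the 95% interval for ab excludes 0. Outcome residual SD is 1. The value a = 0.22 takes f = 0.11 as d = 2f; applying that to a facet slope is an assumption.

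| a | b | N | r = 0.3 | r = 0.5 | r = 0.7 |
|---|---|---|---|---|---|
| 0.5 | -0.5 | 116 | 22% | 50% | 71% |
| 0.22 | -0.5 | 116 | 6% | 12% | 21% |
| 0.22 | -0.5 | 82 | 3% | 5% | 13% |
| 0.22 | -0.3 | 116 | 3% | 6% | 12% |

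These rates are approximate, to within a few percentage points. With both slopes in one model, the inert facet is flagged in at most about 4% of trials.

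**4. Five facets with percentile-bootstrap intervals.** Here a = 0.5, b has size 0.5 for one facet and 0 for the other four, and outcome residual variance is 0.75. An inert facet in its own model is flagged in 4%, 30%, 59% and 76% of trials at r = 0, 0.3, 0.5 and 0.7 with N = 116, and in 4%, 16%, 36% and 56% with N = 82. In the joint model the rates are 3.5% to 4.7% (N = 116) and 3.0% to 3.7% (N = 82). At r = 0.7, power for the acting facet falls from 0.78 to 0.72 (N = 116) and from 0.66 to 0.54 (N = 82).

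**5. If allocation has no direct path to the outcome slope.** The protocol text does not say whether it has one. Without it, a shared treatment effect alone biases b. With a = 0.5 and 1:1 allocation, the variance shared through X is 0.25 × 0.25 = 0.0625, so at r = 0 the inert facet's b is -0.5 × 0.0625/1.0625 = -0.029. That is small, but not zero.

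**The case against.** **The reading is not certain.** Section 2.4.2 also speaks of mediators in the plural and of a combined model, and Figure 2, which would settle it, is not shown. This stands: a multi-mediator model is not excluded. The single mediator, the single product and the one-slot legend still favour separate models. If a joint model is meant, the text needs to say so.

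**H1 is not evidence of bias.** A reader might infer that, because iMBT is expected to raise every facet, the slopes move together and path b must be biased. That does not follow. With allocation in the outcome equation, a common treatment shift leaves the flag rate at about 4% when r = 0. Correlation within arm is what matters, and the protocol reports none.

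**The size is assumed.** A reader might also infer that the plan will usually flag several facets. That holds only for large facet effects and high correlation. With a = 0.22, the acting facet is itself found in only about 12% to 24% of trials, so missing it is the likelier error. This stands.

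**A full joint model is demanding.** Five facets and one outcome with linear growth give 6 × 2 = 12 growth factors, with up to 12 × 13/2 = 78 variances and covariances, for about 81 participants retained. Simpler models are a defensible trade-off. This argues against requiring the five-facet model, not against a two-construct model or a limit on what the one-facet models may claim.

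**It is a secondary question, and some model detail can be left to a SAP.** Both are true. The protocol does, however, describe the mediation model, and as most naturally read that model does not answer the protocol's own question.

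**Conclusion.** The concern holds in conditional form. If facet slopes are correlated within arm, separate one-facet models cannot by themselves show which facet mediates, because each facet's product includes a share of the others' effects (a·r·b for an inert facet). The protocol does not support the flat statement that the trial cannot answer the question: that would need a known correlation and certainty that no joint model is intended.

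Over the assumed range at N = 116 with b = -0.5, an inert facet is flagged in about 6% to 21% of trials if a = 0.22 SD and 22% to 71% if a = 0.5 SD, for r from 0.3 to 0.7. In the matching runs the rates are lower at N = 82. The results rest on observed rather than latent slopes, equal residual variances and a direct path from allocation. The change should be made because it is cheap and alters what the mechanism aim can conclude.

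**What to change.** In section 2.4.2, test H2 in one parallel process model per outcome that holds the monitor slope and the acceptance slope together as parallel mediators. Let their residuals correlate, include the direct path from allocation to the outcome slope, and report a bootstrap interval for each specific indirect effect. Name the FFMQ-SF facets that form each construct, since the model cannot be built without this.

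Keep the one-facet models as descriptive, and state that they do not show which individual facet mediates. The two-construct model separates monitoring from acceptance, not all five facets. A five-facet joint model can be optional and may not be feasible at this size.

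No new data are needed. The cost is somewhat wider intervals for the specific effects and a model that is harder to fit with 116 randomised and about 81 retained.
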